**Change 4:**

***Section 4.1 Study design***

7th paragraph:

Old text:

Pain endpoints will be based on subject-reported outcome data. Pain will be assessed by means of selected questions from the BPI-SF daily for 4 days immediately prior to randomization, in order to stratify subjects by worst pain score (WPS)  $\leq 4$  or  $> 4$ , for the 7 days immediately prior to Dose 1, Day 1, and then for Treatment Arms A and B, daily for 7 days prior to each scheduled dosing visit through Week 24, for the 7 days prior to Weeks 36 and 48 visits and for 7 days prior to each telephone contact at Weeks 28, 32, 40 and 44. For Treatment Arm C, pain data will be collected daily for 7 days prior to each scheduled dosing visit through Week 48. Pain will also be assessed by means of the BPI SF questionnaire for all treatment arms at each clinic visit from Dose 1, Day 1 until

the Week 48 visit and for treatment Arms A and B on the day of each telephone contact at Weeks 28, 32, 40 and 44.

New text:

Pain endpoints will be based on subject-reported outcome data. Pain will be assessed by means of selected questions from the BPI-SF daily for 4 days immediately prior to randomization, in order to stratify subjects by  $WPS \leq 4$  or  $> 4$ , and then daily for 6 days prior to Cycle 1, Day 1 or subsequent visits including telephone contacts, as applicable, plus the day of the visit or telephone contact until Week 48. Pain will also be assessed by means of the BPI-SF questionnaire for all treatment arms at each clinic visit or telephone contact from Dose 1, Day 1 until the Week 48 visit and for treatment Arms A and B on the day of each telephone contact at Weeks 28, 32, 40, and 44.

***Section 7.1.1 Tabulated overview:***

Footnote i, footnote j, and footnote k:

Old text:

- i. When a subject is determined to be eligible, the subject will be trained on daily PRO pain data collection using a handheld device. The subject will then complete the pain assessment daily for 4 days prior to randomization and then ~~for the 7 days prior to Dose 1, Day 1.~~
- j. Pain will be assessed during the screening period daily for 4 days prior to randomization and ~~for the 7 days prior to Dose 1, Day 1, then daily for 7 days prior to each scheduled treatment visit through the end of Week 48.~~ Subjects will complete the daily pain assessment using a handheld device. The daily PRO pain input results should be reviewed at the visit to check for completeness.
- k. For Treatment Arms A and B only, pain data will be collected daily using the handheld device for ~~7 days~~ prior to Week 36 and 48 visits, and daily for ~~7 days~~ prior to each telephone contact at Weeks 28, 32, 40, and 44. For Treatment Arms A and B only the BPI SF and the NCCN FACT-P Symptom Index-17 (NCCN-FACT FPSI-17) questionnaires will be completed on the day of the Week 36 and 48 visits and on the day of each telephone contact at Weeks 28, 32, 40, and 44. Twenty-four (24) hour analgesic use will be collected by the study investigator at Week 36 and 48 Visits and at each telephone contact (in Arms A and B) at Weeks 28 ( $\pm 7$  days), 32 ( $\pm 7$  days), 40 ( $\pm 7$  days), and 44 ( $\pm 7$  days).

New text:

- i. When a subject is determined to be eligible, the subject will be trained on daily PRO pain data collection using a handheld device. The subject will then

complete the pain assessment daily for 4 days prior to randomization and then daily for one week (6 days prior to Cycle 1, Day 1 or subsequent visits, as applicable, plus the morning of the visit).

- j. Pain will be assessed during the screening period daily for 4 days prior to randomization and daily for one week (6 days prior to Cycle 1, Day 1 or subsequent visits, as applicable, plus the day of the visit). Subjects will complete the daily pain assessment using a handheld device. The daily PRO pain input results should be reviewed at the visit to check for completeness.
- k. For Treatment Arms A and B only, pain data will be collected daily using the handheld device for one week (6 days prior to the applicable visit, plus the day of the visit) prior to Week 36 and 48 visits, and daily for one week (6 days prior to the applicable phone call, plus the day of the phone call) prior to each telephone contact at Weeks 28, 32, 40, and 44. For Treatment Arms A and B only the BPI SF and the NCCN FACT-P Symptom Index-17 (NCCN-FACT FPSI-17) questionnaires will be completed on the day of the Week 36 and 48 visits and on the day of each telephone contact at Weeks 28, 32, 40, and 44. Twenty-four (24) hour analgesic use will be collected by the study investigator at Week 36 and 48 Visits and at each telephone contact (in Arms A and B) at Weeks 28 ( $\pm 7$  days), 32 ( $\pm 7$  days), 40 ( $\pm 7$  days), and 44 ( $\pm 7$  days).

#### ***Section 7.1.2.1 Screening Period:***

19th Bullet :

Old text:

- for the 7 days prior to Dose 1, Day 1 (Day 7 will be done on the day of Dose 1, Day 1 of the protocol).

New text:

- for 6 full days prior to the dosing visit plus the morning of the day of the dosing visit prior to Dose 1, Day 1.

#### ***Section 7.1.2.3 Initial visit - Dose 1, Day 1 (Treatment arms A, B, C)***

Last bullet:

Old text:

- Subjects will complete the pain assessment daily for ~~the 7 days~~ prior to Dose ~~2,~~ Day 1.

New text

- Subjects will complete the pain assessment daily for 6 days prior to the dosing visit plus the morning of the dosing visit prior to Dose 1, Day 1

***Section 7.1.2.4 Doses 2 to 6 (Treatment arms A and B) and Section 7.1.2.5 Doses 2 to 12 (Treatment arm C)***

19th bullet:

Old text:

- ~~After each visit, subjects will complete the pain assessment daily for the 7 days prior to next dose, Day 1 or for the 7 days prior to the EOT visit.~~

New text:

- Subjects will complete the pain assessment daily for 6 days prior to the dosing visit plus the morning of the dosing visit

***Section 7.1.2.6 End of treatment visit***

17th bullet:

Old text:

- ~~After the visit, subjects will complete the pain assessment daily for the 7 days prior to the Week 28 telephone contact (Treatment Arms A and B only).~~

New text:

- Subjects will complete the pain assessment daily for 6 days prior to plus the morning of the Week 28 telephone contact (Treatment Arms A and B only).

***Section 7.1.2.7.1 Active follow-up with clinic visits***

6th paragraph, 1st bullet:

Old text:

- Pain will be assessed daily for ~~7 days~~ prior to each telephone contact at Weeks 28, 32, 40, and 44 and the daily PRO pain input data will be reviewed for completeness at the telephone contact.

New text:

- Pain will be assessed daily for 6 days prior to the visit plus the morning of each telephone contact at Weeks 28, 32, 40, and 44 and the daily PRO pain input data will be reviewed for completeness at the telephone contact.

***Section 7.3.4.4 Pain Endpoints:***

Paragraph 3:

Old text:

The screening baseline for pain endpoints will be based on the pre-Dose 1, 7-day pain assessment.

New text:

The screening baseline for pain endpoints will be based on the pre-Dose 1, 7-day pain assessment. (Day 7 will be done on the day of Dose 1, Day 1 of the protocol.)

**Change 5:**

***Section 5.2.1 Withdrawal:***

3rd bullet:

Old text:

- A dose delay of more than 4 weeks (maximum of 8 weeks [~~± 7 days~~] between 2 injections)

New text:

- A dose delay of more than 4 weeks (maximum of 8 weeks between 2 injections)

***Section 6.4.7 Dose Delays:***

Logistical difficulties, Paragraph 3:

Old text:

A dose delay of more than 4 weeks (maximum of 8 weeks [~~± 7 days~~] between 2 injections) will lead to study drug discontinuation.

New text:

A dose delay of more than 4 weeks (maximum of 8 weeks between 2 injections) will lead to study drug discontinuation.

**Change 6:**

***Synopsis - Diagnosis and main criteria for inclusion and 5.1.1 Inclusion Criteria:***

2nd bullet:

Old text:

- c. Serum PSA progression defined as 2 subsequent increases in PSA over a previous reference value (~~a minimum of 2 ng/mL [ $\mu$ g/L]~~) **OR**

New text:

- c. Serum PSA progression defined as 2 subsequent increases in PSA over a previous reference value, with a PSA value of  $\geq 2$  ng/mL at the time of the second increase, OR

**Change 7:**

***Section 6.9.1 Prior therapy:***

3rd bullet:

Old text:

- All other prior medications, including pain medications and taken in the 30 days prior to start of study treatment (Dose 1) will be recorded in the subject's medical record and in the appropriate eCRF. The generic or trade name, indication, dosage, and start and stop dates must be recorded.

New text:

- All other prior medications, including but not limited to pain medications, antibiotics, steroids, bisphosphonates, iron therapy, or radiation therapy taken in the 30 days prior to start of study treatment (Dose 1) will be recorded in the subject's medical record and in the appropriate eCRF. The generic or trade name, indication, dosage, and start and stop dates must be recorded.

***Section 7.2.2 Medical history:***

3rd bullet:

Old text:

Considered relevant to the study up to

New text:

Considered relevant to the study up to 6 months prior to screening: History of fractures, trauma, osteomyelitis, joint and dental infections, cellulitis, edema, arthritis, metabolic bone disease, or limitation of function; history of orthopedic

(e.g., presence and location of prosthetic implants) and non-orthopedic (e.g., ileal conduit) surgery that might affect the results of bone scintigraphy; history of recent scintigraphy, especially with I, Ga, or In.

### Change 10:

***Synopsis – Methodology (14th paragraph), Section 4.1 Design overview (14th paragraph), Section 6.8 Post-study therapy (1st paragraph), Section 7.1.2.8.1 End of active follow-up with clinic visits (3rd paragraph), Section 7.1.2.8.2 End of active follow-up without scheduled clinic visits (3rd paragraph):***

#### Old text:

~~After the active follow-up, subjects will enter the long term follow-up period and will be followed via telephone follow-up at 6-month intervals for investigator-reported, radium-223 dichloride-related SAEs, hematologic toxicity (e.g., myelosuppression / myelofibrosis / bone marrow aplasia), new primary malignancies, and survival up to 7 years after the last dose of radium-223 dichloride or until death. Once a separate extended safety follow-up protocol, for the inclusion of subjects who received radium-223 dichloride in the course of Bayer-sponsored clinical trials, has been implemented, the study subjects surviving after the end of the active follow-up will be transitioned to this separate extended safety follow-up protocol and the current study will be terminated at the time the last study subject is transitioned.~~

#### New text:

All study subjects will be eligible for further follow-up either in this study or in a separate long-term follow-up study for up to 7 years. The separate long-term follow-up study has been set up to follow subjects who received radium-223 dichloride or placebo in the course of Bayer-sponsored clinical trials. The long-term follow-up study has a specific focus on investigator reported, radium-223 dichloride-related AEs and SAEs, hematologic toxicity (e.g., myelosuppression / myelofibrosis / bone marrow aplasia), new primary malignancies including leukemias and solid tumors, and survival for up to 7 years after last dose of radium-223 dichloride or until death. During long-term follow-up, subjects will be contacted every 6 months by telephone. All subjects who transition into this separate long-term follow-up study will require a separate signed informed consent.

Transition of all subjects into the separate long-term follow-up study will begin following the later of primary endpoint completion or 2 years after the last radium-223 dichloride treatment is administered to the last treated subject.

Until the transition to the long term follow-up study begins, some subjects may begin long-term follow-up in this study. This study will end when all subjects have transitioned into the long-term follow-up study or discontinued from this study for another reason (e.g., Consent Withdrawn, Lost to Follow-up).

### ***Section 4.1 Design Overview***

#### ***Added Text:***

**Active follow-up period *with* clinic visits:**

Subjects who discontinue study treatment and who did not have an SSE will enter an active follow-up period with clinic visits. These subjects will be evaluated every 12 weeks ( $\pm$  7 days) for pain endpoints, radiological progression, SSEs, survival, treatment-related AEs and serious adverse events (SAEs), and the initiation of other anti-cancer therapies. In addition, subjects who receive cytotoxic chemotherapy will be followed up for the development of febrile neutropenia and hemorrhage during their chemotherapy treatment and for up to 6 months at a frequency based on local clinical practice. During this period, all occurrences of leukemia, myelodysplastic syndrome, aplastic anemia, and primary bone cancer or any other new primary malignancy must be reported as SAEs, regardless of the investigator's causality assessment.

The active follow-up period with clinic visits extends from the discontinuation of the treatment period until the subject experiences an SSE, can no longer travel to the clinic, receives further treatment with cytotoxic chemotherapy for prostate cancer, other systemic radioisotopes, hemibody EBRT, or other investigational drugs, dies, is lost to follow-up, or withdraws informed consent and actively objects to collection of further data.

**Active follow-up period *without* clinic visits:**

Subjects from the treatment period or the active follow-up period with clinic visits who can no longer travel to the clinical site will be followed for survival, treatment-related AEs and SAEs, SSEs, pain endpoints, and the initiation of other anti-cancer therapies with a phone call every 12 weeks ( $\pm$  7 days). In addition, subjects who receive cytotoxic chemotherapy will be followed up for the development of febrile neutropenia and hemorrhage during their chemotherapy treatment and for up to 6 months at a frequency based on local clinical practice. During this period, all occurrences of leukemia, myelodysplastic syndrome, aplastic anemia, and primary bone cancer or any other new primary malignancy must be reported as SAEs, regardless of the investigator's causality assessment.

The active follow-up period **without** clinic visits extends from the EOT period or the end of active follow-up with clinic visits until the subject experiences an SSE, dies, is lost to follow-up, or withdraws informed consent and actively objects to collection of further data.

The maximum duration of the active follow-up is 7 years from the last dose of radium-223 dichloride received by the subject.

All study subjects will be eligible for further follow-up either in this study or in a separate long-term follow-up study for up to 7 years. The separate long-term follow-up study has been set up to follow subjects who received radium-223 dichloride or placebo in the course of Bayer-sponsored clinical trials. The long-term follow-up study has a specific focus on investigator reported radium-223 dichloride-related AEs and SAEs, hematologic toxicity (e.g., myelosuppression / myelofibrosis / bone marrow aplasia), new primary malignancies, including leukemias and solid tumors, and survival for up to 7 years after last dose of radium-223 dichloride or until death. During long-term follow-

up, subjects will be contacted every 6 months by telephone. All subjects who transition into this separate long-term follow-up study will require a separate signed informed consent.

Transition of all subjects into the separate long-term follow-up study will begin following the later of primary endpoint completion or 2 years after the last radium-223 dichloride treatment is administered to the last treated subject.

Until the transition to the long term follow-up study begins, some subjects may begin long-term follow-up in this study. This study will end when all subjects have transitioned into the long-term follow-up study or discontinued from this study for another reason (e.g., Consent Withdrawn, Lost to Follow-up).

#### ***Section 7.1.2.7.1. Active Follow-up with clinic visits:***

Old text:

The subject should return to the clinic every 12 weeks ( $\pm$  14 days) following the EOT visit until the subject experiences a symptomatic skeletal event or until the primary efficacy analysis matures, whichever occurs first; ~~provided that active follow-up will not last less than 2 years or more than 7 years following the subject's last study treatment.~~

In addition to the visits at Weeks 36 and 48, the subjects in Treatment Arms A and B will receive telephone contacts at Weeks 28, 32, 40, and 44 to assess for possible SSE risks and will continue PRO data collection. Pain data, 24-hour analgesic use, BPI and NCCN-FACT FPSI-17 questionnaires will also be collected as detailed below.

New text:

The subject should return to the clinic every 12 weeks ( $\pm$  14 days) following the EOT visit until the subject experiences a symptomatic skeletal event or until the primary efficacy analysis matures, whichever occurs first. Active follow-up will continue for 2 years in this study and not more than 7 years total including the long term follow-up study (if the subject has signed the ICF).

To the extent possible, subjects discontinuing treatment prematurely should nonetheless complete the Week 8, 16, 24, 36, and 48 clinic visits and any applicable tumor assessments scheduled with respect to treatment start. Similarly, subjects in Treatment Arms A and B should receive Week 28, 32, 40, and 44 telephone contacts at the regularly scheduled time with respect to treatment start.

In addition to the visits at Weeks 36 and 48 (from the start of treatment) the subjects in Treatment Arms A and B will receive telephone contacts at Weeks 28, 32, 40, and 44 (from the start of treatment) to assess for possible SSE risks and will continue PRO data collection. Pain data, 24-hour analgesic use, BPI and NCCN-FACT FPSI-17 questionnaires will also be collected as detailed below.

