### **Change 12:**

***Synopsis - Methodology*** (paragraph 13) and ***Section 4.1 Design overview*** (paragraph 11):

Old text:

~~All safety data will be collected beyond the EOT visit, and subjects will come to the clinic for safety and SSE evaluations every 12 weeks for 2 years of active follow-up. Every effort will be made to follow subjects through clinic visits; however, phone contact will be undertaken for subjects unable to come to the clinic. The active follow-up period will continue for 2 years after the subject's last dose of radium-223 dichloride or until the primary efficacy analysis matures, whichever occurs last.~~

New text:

Following the EOT visit, subjects will enter the active follow-up period and will come to the clinic for selected safety and efficacy evaluations every 12 weeks for at least 2 years following last study treatment. Subjects not experiencing an SSE by 2 years following last study treatment will continue active follow-up until the subject experiences an SSE or the primary endpoint matures, whichever occurs first. During active follow-up, every effort will be made to follow subjects through clinic visits; however, phone contacts will be undertaken for subjects unable to come to the clinic.

**Synopsis - Methodology** (paragraph 14) and **Section 4.1 Design overview** (paragraph 13):

Old text:

After the ~~2-years~~ of active follow-up, subjects will enter the extended follow-up period and will be followed via telephone follow-up at 6-month intervals for investigator-reported, radium-223 dichloride-related SAEs, hematologic toxicity (e.g., myelosuppression / myelofibrosis / bone marrow aplasia), new primary malignancies, and survival up to 7 years after the last dose of radium-223 dichloride or until death. Once a separate extended safety follow-up protocol, for the inclusion of subjects who received radium-223 dichloride in the course of Bayer sponsored clinical trials, has been implemented, the study subjects surviving after the end of the ~~2-years~~ of active follow-up will be transitioned to this separate extended safety follow-up protocol and the current study will be terminated at the time the last study subject is transitioned.

New text:

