#### ***Section 7.1.2.7.2 Active follow-up without scheduled clinic visits***

1st paragraph

Old text:

This period starts when subjects can no longer travel to the clinic or if the subject receives further treatment with anticancer therapies during the follow-up period,

~~including standard doses of prohibited~~ cytotoxic chemotherapy for prostate cancer, including taxanes, estramustine, and mitoxantrone, other systemic radioisotopes (samarium-153, strontium-89, rhenium-186, or rhenium-188), hemibody EBRT, or other investigational drugs. Subjects who cannot travel to the clinic will be contacted by telephone every 12 weeks ( $\pm$  14 days) for 2 years following the last study treatment to determine the following:

New text:

This period starts when subjects can no longer travel to the clinic or if the subject receives further treatment with any of the following anticancer therapies during the follow-up period: cytotoxic chemotherapy for prostate cancer, including taxanes, estramustine, and mitoxantrone, other systemic radioisotopes (samarium-153, strontium-89, rhenium-186, or rhenium-188), hemibody EBRT, or other investigational drugs. Subjects who cannot travel to the clinic will be contacted by telephone every 12 weeks ( $\pm$  14 days) for 2 years following the last study treatment to determine the following:

### Change 33

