| Record chemotherapy for other malignancies               |   |                            |                            |                            |                             |                             |                             |                            |                            |                            |                             |                             |                             |                             |                             |                             |                             |                             |                             |                        | X   | X                    | X  | X                    | X   | X                          |
| Record radium-223 dichloride related AEs and SAEs gg |   |                            |                            |                            |                             |                             |                             |                            |                            |                            |                             |                             |                             |                             |                             |                             |                             |                             |                             |                        |   | X                    | X  | X                    | X   |                            |

b Subjects, their treating health care professional, or caregiver will be contacted every 6 months by telephone. Once a separate, extended safety follow-up protocol, for the inclusion of subjects who received radium-223 dichloride in the course of Bayer sponsored clinical studies, has been implemented, the study subjects surviving after the end of the 2 years of active follow-up will be transitioned to this separate, extended safety follow-up protocol and the current study will be terminated at the time the last study subject is transitioned. Subject data collected at other standard-of-care visits and / or contacts may be used to satisfy study-required data.

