#### **4.4 End of Study**

Old text:

The primary endpoint cut-off will be reached at the later of 1) 135 SSE-FS events in subjects included in Comparison 1 as defined in Section 8.4 below, and 2) 75 SSE-FS events following ~~Week 24~~ in subjects included in Comparison 2 as defined in Section 8.4 below, and 3) the last subject has been followed for 30 days from last treatment. In the event the applicable number of events is not reached, the primary endpoint analysis will mature 7 years after the last subject has received last treatment.

New text:

The primary endpoint cut-off will be reached at the later of 1) 135 SSE-FS events in subjects included in Comparison 1 as defined in Section 8.4 below, and 2) 75 SSE-FS events following the 6th dose in subjects included in Comparison 2 as defined in Section 8.4 below, and 3) the last subject has been followed for 30 days from last treatment. In the event the applicable number of events is not reached, the primary endpoint analysis will mature 7 years after the last subject has received last treatment.

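### Active follow-up, in which SSEs are collected, is limited to 2 years in some sections but runs to SSE, primary endpoint maturity or 7 years in others

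*Protocol*

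**What the plan says.** **Statements that give 2 years**

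- Section 7.1.2.7.1 (new text of Amendment 2): "Active follow-up will continue for 2 years in this study and not more than 7 years total including the long term follow-up study". The same edit removed a clause that had made 2 years the minimum and 7 years the maximum.
- Section 7.1.2.7.2 (new text of Amendment 2): subjects who cannot travel are telephoned every 12 weeks "for 2 years following the last study treatment to determine the following".
- Table 7-1, footnote b (new text of Amendment 3): "the study subjects surviving after the end of the 2 years of active follow-up will be transitioned to this separate, extended safety follow-up protocol".

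**Statements that go beyond 2 years**

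- Section 7.1.2.7.1, the sentence just before the 2-year one: clinic visits continue "until the subject experiences a symptomatic skeletal event or until the primary efficacy analysis matures, whichever occurs first".
- Synopsis and Section 4.1 (Amendment 1, Change 12): "Subjects not experiencing an SSE by 2 years following last study treatment will continue active follow-up until the subject experiences an SSE". Maturity of the primary endpoint, if earlier, is the other stopping point given there.
- Section 4.1 (added by Amendment 2): "The maximum duration of the active follow-up is 7 years from the last dose of radium-223 dichloride received by the subject". For follow-up without clinic visits it gives no 2-year limit; that period runs "until the subject experiences an SSE, dies, is lost to follow-up, or withdraws informed consent and actively objects to collection of further data".
- Section 4.1 (Amendment 2): transition to the separate long-term study starts only at the later of primary endpoint completion or 2 years after the last subject's last treatment.
- The Table 7-1 column heading describes active follow-up as lasting at least 2 years.

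**What depends on the duration**

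- Section 4.4: if the event counts are not reached, "the primary endpoint analysis will mature 7 years after the last subject has received last treatment".
- Table 7-1, footnote e: SSEs are not collected by telephone.
- Section 7.1.2.9.1: long-term follow-up is a telephone contact every 6 months. Its data list includes survival status but not SSEs.

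**The concern.** SSE-free survival (SSE-FS) is the primary endpoint, and the analysis is triggered by event counts. How long SSEs are looked for should therefore be stated once. As written, a site following Section 7.1.2.7.1 or footnote b would end systematic SSE collection 2 years after last dose, while a site following Section 4.1 would continue. Ascertainment of the primary endpoint would then depend on which section a site reads.

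Two further consequences follow from the 2-year reading. First, the clock starts at last dose, which is Week 20 for a subject completing Arm A and Week 44 for one completing Arm C, whereas Comparison 2 counts from the 6th dose in both arms. Second, Section 4.4 allows a wait of up to 7 years for missing events, but in most of that time no SSE would be systematically recorded.

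**Working it through.** **1. The plan's own figure.** Inputs from Section 8.6: 74.9 events, hazard ratio 0.606, 1-sided alpha 0.10. Schoenfeld power is Φ(√74.9/2 × |ln 0.606| − 1.282) = 81.2%; the Freedman form gives 80.0%. The stated 80.6% is reproduced.

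**2. Planning model.** Section 8.6 assumes a median SSE-FS of 9 months with constant hazard, so λ = ln 2/9 = 0.0770 per month. Week 24 is 5.52 months, and survival free of an event to Week 24 is exp(−0.0770 × 5.52) = 0.654. The stated share eligible at that point is 55.35%, so the share not lost is 0.5535/0.654 = 0.847. The implied loss hazard is η = −ln 0.847/5.52 = 0.030 per month. The 132.8 subjects entering Comparison 2 give 66.4 per arm.

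**3. Where a 2-year stop falls.** Taking randomization as the start of treatment:

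| | Last dose | Stop, from randomization | Stop, from Week 24 |
|---|---|---|---|
| Arm A | Week 20 = 4.60 months | 28.60 months | 23.08 months |
| Arm C | Week 44 = 10.12 months | 34.12 months | 28.60 months |

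The gap between arms is 44 − 20 = 24 weeks, on the 6th-dose scale as well.

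**4. Events available at the fallback.** Expected events per arm are 66.4 × a/(a+η) × [1 − exp(−(a+η)T)], with a = λ in Arm A and 0.606λ = 0.0467 in Arm C. T is the follow-up time after Week 24.

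- Arm A: 66.4 × 0.719 = 47.7 without a stop. With the stop, 47.7 × (1 − 0.084) = 43.7.
- Arm C: 66.4 × 0.608 = 40.3 without a stop. With the stop, 40.3 × (1 − 0.111) = 35.9.
- Total: about 88 against about 80, a loss of about 8.5. Schoenfeld power falls from 85.7% to 83.0%.
- With no dropout (η = 0): about 132 against 104, a loss of about 28.

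**5. Events at the expected cut-off.** Section 8.6 (Amendment 1) expects cut-off at 39 months on average. Accrual is not given in the text available, so uniform accrual over 12 to 30 months is assumed.

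| Accrual | Implied dropout: no stop / stop | No dropout: no stop / stop |
|---|---|---|
| 12 months | 80.3 / 78.6 | 105.9 / 102.1 |
| 18 months | 77.4 / 76.3 | 100.1 / 97.6 |
| 24 months | 73.0 / 72.1 | 92.6 / 90.7 |
| 30 months | 66.2 / 65.5 | 82.6 / 81.1 |

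The loss is 0.7 to 1.7 events with the implied dropout and 1.5 to 3.8 with none. Power changes by less than 1 percentage point in every row.

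**6. Chance of never reaching 75.** Since Amendment 3 the trigger counts events after the 6th dose. Simulating the same model from Week 20, mean available events fall from about 98 to 89, and the chance of fewer than 75 rises from about 0.1% to about 2%.

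**7. Direction of the error in steps 4 to 6.** These calculations stop all events at 2 years, deaths included. The protocol collects survival for up to 7 years after last dose, so the losses and the 2% are upper bounds. How far below them the truth lies cannot be computed, because the text available does not split SSE-FS events into SSEs and deaths.

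**8. Unequal ascertainment.** Between 24 months and 24 months plus 24 weeks after the 6th dose, the 2-year rule leaves Arm A completers observed for deaths only, while Arm C completers are still observed for SSEs and deaths. If deaths in that window are counted, recorded events are understated in Arm A alone, which works against the extended regimen.

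**The case against.** Much of the protocol supports reading 2 years as a floor: the Table 7-1 heading, the sentence before the disputed one, and the rules in Section 7.1.2.6.1 (Amendment 1) and footnote ee for subjects who cannot travel or who start other anticancer therapy after 2 years. Those rules make sense only if active follow-up can run longer. Section 7.1.2.6 also requires SSEs found at unscheduled visits to be recorded for subjects in active follow-up. On this view the point is loose drafting, not a decision to end event collection. That is fair as to intent. It does not remove the contradiction, because two other places also say 2 years and no later change shown corrects them.

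A reader might infer that the 7-year fallback would be empty. The documents do not support this. Events from the first 2 years remain in the analysis, and survival is collected for up to 7 years. Deaths therefore keep accruing, provided death counts in SSE-FS, as its name and the phrase about surviving SSE-free imply. Only late SSEs are at risk.

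A reader might also infer a serious risk of missing the trigger: from the 24-week landmark of Section 8.6, the chance of never reaching 75 rises from 3% to 24%. That landmark no longer governs the trigger. On the 6th-dose count the figure is at most about 2%, and expected events stay above 75 even with the stop.

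Finally, the wording cited comes from the amendment history. The current body sections and the tracked text of Amendment 4 were not available. Amendment 4 touched several of the same sections, with fracture reporting as the main stated reason, so a correction there cannot be excluded.

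**Conclusion.** The contradiction is real and stands in adopted amendment text. Its likely effect on the planned analysis is small: about 1 to 4 of roughly 75 Comparison 2 events at 39 months. It matters more if the fallback is used, where at most about 8.5 events (implied dropout) to 28 (none) would be lost and the added years would bring mainly deaths. The stronger reason to resolve it is consistency: the 2-year reading makes SSE ascertainment differ between sites, and between Arms A and C on Comparison 2's own time scale.

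The figures rest on exponential SSE-FS with the Section 8.6 parameters, the dropout backed out of the 55.35%, completed dosing on schedule, and accrual assumed at 12 to 30 months. Comparison 1 was not quantified, because its assumed effect is not in the text available.

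**What to change.** First confirm in the current body text, including Amendment 4, that the three 2-year statements still stand. If they do:

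- **Sections 7.1.2.7.1 and 7.1.2.7.2:** state that, for subjects without an SSE, active follow-up with SSE collection continues in this study beyond 2 years after last dose until an SSE or primary endpoint completion, to a maximum of 7 years. For subjects on telephone follow-up, say how a suspected SSE is confirmed at the clinic, since footnote e excludes collection by telephone.
- **Table 7-1, footnote b:** state that transition starts at the later of primary endpoint completion or 2 years after the last subject's last treatment, as in Section 4.1.

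This is wording only. The added work is continued 12-weekly contact for the few subjects still event-free and followed at 2 years. On the planning assumptions these are about 8% of Comparison 2 subjects in Arm A and 11% in Arm C, or roughly 6 and 7 of 66 per arm. Section 4.1 already calls for following them.
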